114 intervention and at 6- and 12-month follow-up.

115 The primary hypothesis that will be tested is that the program will be feasible and effective in
116 increasing the psychological functioning of the person.

117 The secondary hypothesis will test whether participants assigned to the experimental condition will
118 show a reduced level of stress, anxiety, depression, and fear of COVID-19, as well as improved
119 emotion regulation strategies, self-efficacy, and psychological well-being than those in the WL
120 condition at treatment termination.

121 Moreover, participants in the experimental condition will be expected to present maintained outcomes
122 or further decreased psychological symptoms at 6 and 12-month after the end of the treatment
123 program.

124 **METHODS**

125 **Design**

126 The project consists of a prospective, randomized, open, and parallel group-controlled study with two
127 arms: an experimental arm with 8 online weekly CBT self-help sessions, and a waiting list (WL)
128 control arm.

129 **Ethical Statement**

130 The study was approved by the Ethical Committee of the Catholic University of Milan, Italy (ID: 25-
131 21). All procedures performed in the study will be run following the ethical standards of the
132 institutional and/or national research committee and with the Helsinki Declaration and its later
133 amendments or comparable ethical standards.

134 **Patients and public involvement**

135 Participants from the general population will be recruited through advertisements placed on social
136 media platforms (i.e., Facebook, Instagram, Twitter), and online webinars on the topic.
137 The recruitment materials will include details about the study aim, the treatment delivered, and the
138 conditions for participation, together with the weblink to access the program.

139 Inclusion criteria for the participants into the study will be: (A) being fluent in the Italian language;
140 (B) being over 18 years old; (C) providing online informed consent; and (D) showing
141 mild/subthreshold levels of symptoms at the 12-Item General Health Questionnaire (GHQ-12) -
142 Italian version (50, 51) - the most extensively used screening tool assessing the severity of common
143 mental disorders over the past few weeks using a 4-point Likert-type scale (from 0 to 3). Its total
144 score ranges from 0 to 36, with high scores indicating worse health status. Only participants who

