145 score ≥ 15 on the GHQ and show moderate levels of symptoms at the clinical interview will be
146 included in the study.

147 Participants will be excluded from the program if: (A) presenting visual, hearing, or cognitive
148 impairments that will prevent them from receiving and following the intervention; (B) suffering from
149 severe psychiatric disorders according to the Diagnostic and Statistical Manual of Mental Disorders
150 (DSM 5) (52); (C) lacking basic computer skills or internet access.

151 Respondents will not be excluded if already receiving psychopharmacological therapy or
152 psychological-psychotherapeutic support.

153 **Sample size calculation**

154 The minimum sample size required to conduct this study was calculated using an a priori sample size
155 calculator (G*Power 3.1.9.2 software) for *F* tests (53-55). Participants were randomly divided into
156 two groups: (A) iCBT self-help and (B) waiting list control. Moreover, participants will be measured
157 in 3 moments: (1) before the intervention, (2) at the end of intervention (two months later), and (3)
158 after 12 months from treatment termination. Due to the novelty of the study from which to derive
159 realistic estimates of effect sizes, the partial η^2 was set a priori to assume a value of 0.02 – small
160 effect size (56, 57) – which provides a Cohen's *f* value of 0.143. Moreover, the type I error (α) rate
161 was set at 0.05 (two-sided) and the Power ($1 - \beta$) was set at 0.95, and the a priori correlation between
162 repeated measures was set at 0.50, according to general guidelines (56). Lastly, the non-sphericity
163 correction was set to 1. Results showed that there is a 95% chance of correctly rejecting the null
164 hypothesis of no significant effect of the interaction with 128 participants in total (64 for each group).

165 **Randomization and blinding**

166 The random randomization scheme will be generated using the Web site Randomization.com (58).
167 Allocation concealment will be ensured by the program generating an anonymous code for each
168 participant that will be associated with the randomization sequence. Due to the nature of the
169 intervention, the treatment group allocation cannot be concealed from the participants, nor the
170 research team and assessor of outcomes. Participants will be assigned to one of two conditions within
171 2 working days from their baseline assessment (Figure 1).

172

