173 *** PLEASE INSERT Figure 1: Flow chart of the RinasciMENTE study

174 **Measures**

175 *Demographic and clinical information.* Information about age, gender, education, civil status, weight, and
176 high - used to calculate the Body Mass Index (BMI, kg/m²) in presence of dysfunctional eating behaviors
177 - will be self-reported online at baseline. Subjects will be also asked to provide information about the
178 country where they are currently living, their work situation (before and after the COVID-19 pandemic),
179 and the personal experience they made of both COVID-19 pandemic and related preventive measures.
180 The Italian version of the following psychological measures will be also collected at baseline (T0),
181 treatment termination after 2 months (T1), at 6-month (T2), and 12-month (T3) follow-up in the
182 experimental condition only). Please see Figure 2 for a detailed project timeline.

183 *** INSERT GANTT Figure 2: Gant of the RinasciMENTE study

184 Primary outcome:

185 *Outcome Questionnaire (OQ-45)* (59) composed by 45 items rated on a 5-point Likert scale (0 = Never –
186 4 = Almost always) assessing the treatment progresses across 3 different domains: Symptom Distress (SD
187 – 25 items: 2, 3, 5, 6, 8, 9, 10, 11, 13, 15, 22, 23, 24, 25, 27, 29, 31, 33, 34, 35, 36, 40, 41, 42 and 45),
188 Interpersonal Relations (IR – 11 items: 1, 7, 16, 17, 18, 19, 20, 26, 30, 37 and 43), and Social Role (SR –
189 9 items: 4, 12, 14, 21, 28, 32, 38, 39 and 44). The OQ-45 total score is calculated by summing the score of
190 the three subscales. Total score (range 0 to 180) is calculated by the sum of the items.

191 *Secondary outcomes:*

192 *Perceived stress scale* (PSS) (60), composed of 10 items rated on a 5-point Likert scale (from 0 = never to
193 4 = very often) assessing the degree to which situations in one's life are appraised as stressful. PSS scores
194 are obtained by reversing responses (i.e., 0 = 4, 1 = 3, 2 = 2, 3 = 1 and 4 = 0) to the four positively stated
195 items (items 4, 5, 7, and 8) and then summing across all scale items. The total score (range 0 to 40) is
196 calculated by the sum of the items.

197 *Emotional regulation questionnaire (ERQ)* (61), composed of 10 items rated on a 7-point Likert scale
198 (from 1 = strongly disagree to 7 = strongly agree) assessing respondents' tendency to regulate their

199 emotions in two ways: Cognitive Reappraisal (items 1, 3, 5, 7, 8, and 10) and Expressive Suppression

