281 communicating the update of the new material on the platform. Participants who will not access the
282 material or that will not complete the suggested tasks and exercises will receive a weekly reminder
283 containing a brief encouraging message every Monday.

284 At the end of the program (after two months – T1), participants in both conditions will be asked to
285 fill in the baseline questionnaires again. Then, the experimental group will be also assessed after 6-
286 and 12 months from the term of the treatment (T2 and T3) (Figure 1).

287 **Statistical analysis**

288 Statistical analyses were performed using SPSS software ver. 24.0 (76).

289 First, preliminary analyses will be performed to test the assumptions of both univariate and
290 multivariate normality: if (strong) violations will be detected, robust methods or data transformation
291 will be applied. Dropouts will be excluded from the study.

292 A missing values analysis will be run to see if the values are Missing Completely at Random
293 (MCAR), or if there is some pattern among missing data. If there are no patterns detected, then
294 pairwise or listwise deletion will be done to deal with missing data. However, if the missing values
295 analysis detects a pattern, then imputation will be done.

296

297 The demographic characteristics will be reported as means and standard deviations for continuous
298 variables, and frequencies and percentages for categorical variables.

299 The chi-square statistic will be used to test the association between treatment groups and socio-
300 demographic and variables (i.e., age, gender, education, civil status, job), and correlation analysis
301 will be used to test the association between quantitative variables.
302 The outcomes will be compared in the two treatment conditions using an Intention-To-Treat (ITT)
303 approach. The significance level will be set at 5%.
304 A repeated-measures ANOVA will be used to determine whether there are any between and within
305 groups differences in the selected outcomes from baseline to treatment termination. , Then repeated-
306 measures within group ANOVA will test outcome differences over time baseline, end of treatment,
307 6- and 12-month follow-up) in the experimental group only (. Corrected effect sizes (Cohen's *d*) and
308 significance at 95% confidence interval (95% CI) will be calculated for both between-group and

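### The secondary hypothesis is tested on about 8 to 12 scores at an unadjusted 5% with no decision rule; separately, the plan does not say which OQ-45 score is confirmatory

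*Combined protocol and SAP*

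**What the plan says.** The last paragraphs of the Background separate a primary hypothesis (feasibility, and effectiveness for psychological functioning) from a secondary one. The latter opens "The secondary hypothesis will test whether participants assigned to the experimental condition will" and goes on to name stress, anxiety, depression, fear of COVID-19, emotion regulation, self-efficacy and well-being, compared with the waiting list at the end of treatment.

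The Measures section places the OQ-45 alone under the primary outcome. It describes three domains and defines a total running from 0 to 180. Six instruments follow as secondary outcomes: PSS, ERQ, DASS-21, FCV-19S, GSES and WHOQOL-BREF.

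Under Statistical analysis, the selected outcomes are compared between arms from baseline to treatment termination by repeated-measures ANOVA, and "The significance level will be set at 5" per cent. Sidedness is stated only under Sample size calculation, where the type I error rate "was set at 0.05 (two-sided"). That section does not name the OQ-45. Correlation analysis "will be used to test the association between quantitative variables"; the variables are not listed. The plan contains no multiplicity adjustment, testing order or rule for declaring the secondary hypothesis met.

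**The concern.** A 5% level applied to each score is not a 5% level for a hypothesis that covers many scores. It would matter less if the secondary outcomes were labelled exploratory, but the plan calls them a hypothesis to be tested. The opening of the Discussion words the study objective in terms of stress, anxiety, depression, fear, emotion regulation and self-efficacy without mentioning the OQ-45, and Expected results repeats these constructs as what the trial should show. The effectiveness message therefore leans on the set of tests that has no error control. Because the plan does not say how many positive scales are needed, one or two significant results could be read as confirmation, and nothing in the text prevents that.

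The second gap concerns the primary outcome. With a total and three domains available, and no sentence choosing between them, four results could be put forward as the primary one.

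**Working it through.** **1. The plan's own figure.** Inputs from Sample size calculation: f = 0.143, 2 groups, 3 measurements, correlation 0.50 between repeated measures, sphericity correction 1, α = 0.05, power 0.95. For the group-by-time interaction, λ = f²·N·m/(1 − ρ) = 0.143² × 128 × 3 / 0.5 = 15.70, with 2 and 252 degrees of freedom. Power is 0.951 at N = 128 and 0.948 at N = 126. The stated 128 is reproduced. It is a calculation for one outcome at 5%.

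**2. Counting the secondary scores (Measures section).**
- 8 scores: PSS, three DASS-21 scales, FCV-19S, GSES, one ERQ score, one WHOQOL-BREF score.
- 12 scores: the same with two ERQ strategies and four WHOQOL-BREF domains (8 − 2 + 6).
- 6 scores: instrument totals only.

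The plan does not state a count; these are readings of how it scores the instruments.

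**3. Chance of at least one significant difference in either direction, with no true effect.** With two arms and two time points, each interaction test has one numerator degree of freedom and is non-directional. For independent scores the chance is 1 − 0.95^k: k = 8 gives 0.337, k = 12 gives 0.460, k = 6 gives 0.265. For correlated scores, equally correlated normal test statistics were integrated numerically. The documents give no inter-score correlations, so these are assumptions.

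| Scores | r = 0 | r = 0.5 | r = 0.7 |
|---|---|---|---|
| 6 | 26.5% | 20.7% | 16.4% |
| 8 | 33.7% | 25.0% | 19.1% |
| 12 | 46.0% | 31.9% | 23.2% |

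**4. Chance of at least one apparent improvement.** A two-sided 5% test errs in the favourable direction 2.5% of the time. For independent scores the chance is 1 − 0.975^k.

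| Scores | r = 0 | r = 0.5 | r = 0.7 |
|---|---|---|---|
| 6 | 14.1% | 10.4% | 8.2% |
| 8 | 18.3% | 12.5% | 9.5% |
| 12 | 26.2% | 16.0% | 11.6% |

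For 8 to 12 scores, against 2.5% for one test, this is about 4 times (9.5/2.5 = 3.8) to 10 times (26.2/2.5 = 10.5).

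**5. Price of formal control.** The between-arm analysis uses two measurements. With the planned effect (partial η² = 0.02, so f² = 0.02/0.98), λ = (0.02/0.98) × 128 × 2 / 0.5 = 10.45. With 64 per arm this is a difference in change of √10.45 / √32 = 0.57 SD. From the noncentral t with 126 degrees of freedom:
- α = 0.05: power 0.894.
- Holm's first step, 8 scores (0.05/8 = 0.00625): power 0.674.
- Holm's first step, 12 scores (0.05/12 = 0.00417): power 0.623.

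If a primary result with the same effect must be significant first, the 8-score figure becomes about 0.60 to 0.66 for correlations of 0 to 0.7 between the two tests.

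**The case against.** Several counter-arguments have force.

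- **The scores overlap.** Stress is measured by both the PSS and the DASS-21, and subscales of one questionnaire are counted separately. Independence is therefore implausible, and the upper ends of the ranges are limits, not best guesses. This stands, and is why the values at 0.5 and 0.7 are shown.
- **The hypothesis can be read as a conjunction.** Its outcomes are joined as a list, and no sentence says that one positive scale suffices. If all had to be met, the any-one error rate would not be the relevant quantity. This is fair, but the plan does not say that all must be met either; the missing rule is the defect.
- **Secondary outcomes often go unadjusted.** That is acceptable when they are supportive. Here they are named as a hypothesis and carry the stated objective.
- **The OQ-45 total is the natural primary score.** It is the only OQ-45 score given a range, and its calculation is stated twice. This is probably the intended reading, and one sentence would settle it.
- **The correlations are peripheral.** They appear with the socio-demographic comparisons and are not tied to an efficacy claim. Accepted; they are not counted in the figures.

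A reader might infer that an ineffective programme has a 25-46% chance of showing an improvement. The calculation does not support that: this range counts differences in either direction, while the hypothesis is directional. A reader might also infer that the undesignated OQ-45 score causes these rates. It does not, because the OQ-45 is not among the 8 to 12 secondary scores.

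**Conclusion.** The point holds in two separate parts.

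First, the plan does not hold a 5% error rate for its secondary hypothesis if any single positive score may count. With no true effect, at least one significant difference in either direction has a chance of about 25-34% for 8 scores and 32-46% for 12 (correlations 0.5 to 0), or 19% and 23% at 0.7. At least one apparent improvement has a chance of 12.5-18% and 16-26%, or 9.5% and 12% at 0.7. These figures rest on the score counts above and on assumed equal correlations. A false improvement is thus materially more likely than the nominal level suggests, but it is not the expected outcome.

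Second, the confirmatory OQ-45 score is not named. This is a gap in specification. It does not mean that the trial's primary claim rests on the secondary scales: the OQ-45 is the sole primary outcome and has its own hypothesis.

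**What to change.** Add to the Statistical analysis section:

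1. The between-arm comparison of the OQ-45 total from T0 to T1 is the only confirmatory test, at two-sided 5%.
2. The secondary scores come from a fixed list that settles which ERQ, DASS-21 and WHOQOL-BREF scores are used. These scores, the OQ-45 domains, the correlations and the single-arm T2 and T3 results are reported as supportive estimates with 95% confidence intervals. They cannot by themselves support a claim of effectiveness.
3. Only if the sponsor wants formal secondary claims: test the between-arm T0-T1 contrasts on that list after a significant primary result, using Holm's procedure.

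Items 1 and 2 cost wording only and add no participants, visits or measures; the effect sizes and intervals are already planned. They do limit what the trial can claim from the secondary scales. Item 3 is a trade-off: at a 0.57 SD difference in change, power for one scale at the first Holm step falls from 0.89 to about 0.67 with 8 scores, or 0.62 with 12, and somewhat lower once the primary gate is counted. Later Holm steps are less strict. Power for the primary test is unchanged under all three items.

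### The only test named for the 6- and 12-month visits is an overall within-arm F that includes baseline, so it cannot show whether gains are maintained

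*Combined protocol and SAP*

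**What the plan says.** **Hypothesis.** The last hypothesis in the Background section reads "Moreover, participants in the experimental condition will be expected to present maintained outcomes", or a further decrease in symptoms, at 6 and 12 months after the program ends. The natural reference for maintenance is end of treatment (T1).

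**Test.** Under Statistical analysis, the between-arm comparison runs from baseline to treatment termination. For the later visits the plan states that repeated "measures within group ANOVA will test outcome differences over time baseline, end of treatment", with "6- and 12-month follow-up) in the experimental group only". That is one F over four visits (T0, T1, T2, T3) in one arm. The Measures and Procedure sections confirm that only the experimental arm is assessed at T2 and T3.

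**Other output.** The same section plans "Corrected effect sizes (Cohen's *d*) and" 95% confidence intervals, for both between-group and within-group differences, and Cohen's f for the total effect. It does not say which pairs of visits the within-group d compares. It names no follow-up contrast, post-hoc comparison or maintenance margin.

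**Assumption checks.** The section says "preliminary analyses will be performed to test the assumptions of both univariate and" multivariate normality. Sphericity is not mentioned there. It appears only under Sample size calculation, where "the non-sphericity" "correction was set to 1" for a two-group, three-visit interaction.

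**The concern.** Maintenance is a statement about T2 and T3 relative to T1. An overall F over T0 to T3 asks something else: whether any of the four means differ. If treatment produces a drop from T0 to T1, that drop alone can make the F significant, whatever happens afterwards.

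Durability is one of the trial's stated hypotheses, and no control arm is measured at T2 and T3, so this within-arm analysis is the only evidence on it. If the visit pairs are left open, a report could give a significant time effect and changes from baseline, comply fully with the plan, and never compare follow-up with end of treatment.

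**Working it through.** **1. The plan's own figure.** Inputs from Sample size calculation: partial eta-squared 0.02, alpha 0.05, power 0.95, correlation 0.50, non-sphericity value 1, two groups, three visits.

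- f² = 0.02/0.98 = 0.0204, so f = 0.143.
- Noncentrality = f²·N·m/(1 − rho) = 0.0204 × 128 × 3/0.5 = 15.67, on 2 and 252 degrees of freedom.
- Power = 0.951.

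The stated 128 (64 per arm) is reproduced. It belongs to the group-by-time interaction, not to the four-visit within-arm test.

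**2. The four-visit F for kept and lost gains.** Inputs: n = 64 and rho = 0.5 from the plan; the gain d, in SD units, is assumed. With equal correlations and variances, noncentrality = n·S/(1 − rho), where S is the sum of squared deviations of the four visit means from their average. Degrees of freedom are 3 and 3(n − 1) = 189.

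- Fully kept (0, −d, −d, −d): the average is −0.75d, so S = (0.75d)² + 3(0.25d)² = 0.75d².
- Fully lost at both follow-ups (0, −d, 0, 0): the average is −0.25d, so S = (0.75d)² + 3(0.25d)² = 0.75d².

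The two are identical, so the power is identical for every n, d and rho under this structure. Cohen's f for the total effect is √(S/4) = 0.433d in both cases, so it does not separate them either.

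| Assumed gain d | Noncentrality, 0.75 × 64 × d²/0.5 | Power, fully kept | Power, fully lost |
|---|---|---|---|
| 0.20 | 3.84 | 34% | 34% |
| 0.33 | 10.45 | 77% | 77% |
| 0.50 | 24.0 | 99% | 99% |
| 0.61 | 35.3 | over 99.9% | over 99.9% |

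The last row is the gain implied by the plan's f if it is kept at both post-baseline visits of the sized design: interaction f² = d²/18, so d = 0.143 × √18 = 0.61.

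Gradual relapse (0, −d, −d/2, 0) gives S = 1.25d² − (1.5d)²/4 = 0.6875d². At d = 0.5 the noncentrality is 22.0 and the power 98%, against 99% for full maintenance.

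**3. A contrast that does separate them.** For T3 minus T1, the standard error is √(2(1 − rho)/n) = √(1/64) = 0.125 SD. At d = 0.5, a paired test is significant in 98% of trials if the gain is lost and in 5% if it is kept. The documents give no dropout rate, so the numbers of completers below 64 are assumed:

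| Completers | 95% CI half-width, T3 − T1 |
|---|---|
| 64 | 0.25 SD |
| 48 | 0.29 SD |
| 40 | 0.32 SD |

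**4. Sphericity (secondary).** Follow-up is counted from the end of a two-month program, so the visits fall at about 0, 2, 8 and 14 months. Assume that the correlation is 0.7, 0.8 or 0.9 at two months and decays exponentially with time; epsilon is then 0.79, 0.72 or 0.65. In 40,000 simulated trials per pattern with n = 64 and no true change, the uncorrected F rejected in 6.2%, 6.5% and 7.3%. With the Greenhouse-Geisser correction the rates were 4.8%, 4.8% and 4.9%. With equal correlations of 0.5 the uncorrected rate was 5.0%.

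**The case against.** **The plan already has pairwise output.** Cohen's d compares two means, and a within-group d with a 95% confidence interval is planned beside the overall effect. This stands: a reader might infer that the plan has no means of comparing follow-up with end of treatment, and that would be too strong. The gap is that the pairs are not specified, so T0–T1, T0–T2 and T0–T3 would satisfy the text.

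**No decision rule equates a significant F with maintenance.** Also correct. The plan says only that the ANOVA tests differences over time. A reader might infer that a trial with complete relapse would be declared a success; the documents do not say that. What remains is that the one named test does not address the hypothesis.

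**The F is not always significant.** True. At a gain of 0.2 SD its power is only 34%. The exact claim is equal power for kept and lost gains.

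**The plan does not say the ANOVA will be uncorrected.** A reader might take the value of 1 as a decision to assume sphericity in this analysis. It is a sizing input for a different test. The analysis section is silent, and the 6–7% error rate depends both on using an uncorrected F and on an assumed decay of correlations. Unequal spacing makes such decay plausible, not certain.

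**Scope.** The between-arm comparison at treatment termination is unaffected. That limits the weight of the point but does not answer it.

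**Conclusion.** The concern holds. The named follow-up test cannot answer the maintenance hypothesis: under equal correlations its power is the same for gains fully kept and gains fully lost at both follow-ups (99%, 77% and 34% at assumed gains of 0.5, 0.33 and 0.2 SD, with n = 64 and correlation 0.5). The equality is algebraic; the particular percentages rest on the assumed gains. A sphericity correction would not change this, because a corrected overall F still includes the change from baseline.

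The missing sphericity correction is a lesser matter: a type I error of about 6–7% instead of 5%, conditional on an uncorrected F and decaying correlations.

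A reader might also infer that a non-significant T3 minus T1 difference would establish maintenance. It would not. With a half-width of 0.25 to 0.32 SD, such a result can be compatible with loss of a material part of the gain. A margin is needed, and the documents give none.

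**What to change.** Amend Statistical analysis as follows.

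1. Name T2 minus T1 and T3 minus T1 in the experimental arm, with 95% confidence intervals, as the maintenance estimates. Name the same visit pairs for the within-group Cohen's d.
2. State a maintenance margin in advance, chosen and justified by the sponsor, and judge maintenance by where the confidence interval lies relative to it, not by a non-significant difference.
3. Estimate the contrasts from a linear mixed model with visit as a categorical factor and unstructured covariance, using all available visits. If the ANOVA is kept, apply the Greenhouse-Geisser correction and report the same contrasts.
4. Describe the result as within-arm and uncontrolled.

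The cost is a few lines of text, slightly more analysis work and the need to commit to a margin. No extra visits or data are required.
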